## **Specific Aims**

### **Aim 1**

Feasibility of measuring language and memory functions in pediatric epilepsy with MEG brain signals.

### **Aim 2**

Characterize language and memory circuitry in pediatric epilepsy subjects with seizure focus from the right or left hemispheres.

## **Study Design and Procedures**

This is a pilot research study where we will design, develop and implement language and working memory tasks to study brain activities from children with epilepsy. Specifically For language assessment, a well known MEG language protocol will be used and novel signal processing techniques will be applied. We will use a design and implement a newwidely utilized paradigm to study memory function and adapt signal-processing techniques from previous literature for the processing and analysis of MEG signals collected during memory task. We will perform a MEG scan and collect data from ten pediatric subjects with drug-resistant focal epilepsy

Title: Pediatric Language and Memory Mapping in Refractory Epilepsy using Magnetoencephalography

PI: [name]

Site: Arkansas Children's Hospital

under evaluation for resective surgery. If a MRI scan is available from medical records and images have the appropriate characteristics for MEG (see more specifications at MRI section) analysis, we will use MRI for MEG source reconstruction. If MRI is not available, we will perform one scan. MRI is necessary to obtain brain anatomy for high quality MEG source reconstruction. Quantitative parameters will be extracted from MEG data for evaluating language and memory functions. This is a pilot [research](#) study where we will test the feasibility of the recording of both standard language and [experimental-well-known](#) memory task in patients with epilepsy. This research is important to investigate, by a non-invasive means, possible patterns of language and memory organization that may in future guide surgery and limit potential loss of these functions.

## **Study Population**

A total of fifteen (15) pediatric patients with drug-resistant focal epilepsy under evaluation for resective surgery will be recruited from the comprehensive epilepsy program of the Arkansas Children's Neuroscience Center. If the patient is eligible, they will be informed about this study during their routine clinic visits by their clinician, and asked if they are interested in participating. Those who express an interest will be provided with the informed consent form (ICF) approved by the UAMS Institutional Review Board (IRB). If they agree to participate, they will be scheduled for the research visit. Subjects will be compensated with a gift card of \$40 which will be given to the parent or guardian (for subjects under 18) or to the subject (if over 18) after completion of study procedures.

### ***Inclusion Criteria***

- 8 to 21 years old
- Drug-resistant focal epilepsy
- Enrolled in the Arkansas Children's Neuroscience Center Comprehensive Epilepsy Program
- Under evaluation for resective surgery
- English speakers. This is not a treatment/intervention study.

### ***Exclusion Criteria***

- Previous resective surgery for epilepsy
- Presence of progressive neurodegenerative disorders
- Presence of significant magnetic artifacts; electronic, magnetic or metallic implants (e.g. pins, screws, shrapnel remains, surgical clips, artificial heart valves, cochlear implants, vascular stents pacemakers); or permanent make-up or tattoos made with metallic dyes
- Presence of seizures within 24 hours of the MEG
- Use of sedation during the MEG acquisition
- Inability to be in a seated or supine position during the tasks
- Major medical disorders (e.g. HIV, cancer)
- Significant visual or auditory disabilities
- Physical disabilities that interfere with accomplishment of study tasks (when applicable)
- Claustrophobia, or fear of cramped or confined spaces
- Pregnancy or suspected pregnancy
- Any condition that the investigator feels might put the patient at risk

Title: Pediatric Language and Memory Mapping in Refractory Epilepsy using Magnetoencephalography

PI: [name]

Site: Arkansas Children's Hospital

## **MEG Acquisition**

Each subject will have one MEG session with the recordings of baseline resting state, language and memory protocols. Subjects will have a break period between the language and memory tasks. MEG recordings will be acquired for approximately 35 minutes. The subject will be allowed to practice the language and memory tasks before the MEG recording to feel familiar with them. This practice phase will be a short version of the task administered by a computer and will take approximately 6 minutes.

## ***MEG System Equipment***

Arkansas Children's Hospital (ACH) hosts the only one of its kind in the state and latest-generation whole-head MEG system (TRIUX™ neo, see Fig. 1A) with helium recycling technology for zero helium boil-off. MEG system is a clinical device with Food and Drug Administration (FDA) approval. The MEG system consists of 306 (see Fig. 1C) Superconducting Quantum Interference Devices (SQUIDs). The MEG scan is located inside of a magnetically shielded room (MSR, see Fig. 1D) to reduce environmental noise to a level compatible with the brain signals. The MEG system is equipped with a specially designed bed (Fig. 1A) and chair (Fig. 1B) for supine and seated measurements (reclined and upright). MEG laboratory is equipped with an audio-video surveillance and communication system, and additional electronics to design specific protocols to record MEG in response to external stimuli. Because exact information about the relative position of the head with respect to the sensor array is necessary for post-analysis, MEG laboratory is equipped with "head position indicator" coils and digitization system to determinate this relative position. The 3-dimensional (3D) digitization system is used in the preparation phase before MEG measurements to digitize the positions of the coils as well as the landmarks on the head. The locations of the landmarks are used to establishing a coordinate transformation between MEG and the anatomical information.

## ***MEG Preparation Phase***

The subject will be first seated in a chair outside of the MSR. One pair of electrooculogram (EOG) electrodes will be attached to the lower corner of the left eye and upper corner of the right eye to measure eye blinks. Electrocardiogram (ECG) electrodes will be attached to the chest. Five head position indicator coils will be attached to the head. Three landmarks (left and right preauricular points, and nasion) and the five HPI coils will digitize along with ~200 additional points of the head surface with an electromagnetic 3D digitizer (Polhemus Fastrak®). We will take pictures with an ACH camera (e.g. standalone camera, tablet or phone device) of the three landmarks and MEG coils. Pictures will be used to guide the coregistration between MRI and MEG for source analysis and to know precisely where each of the MEG coils and points are located in relation to the head. Next, the subject will be placed under the MEG helmet.

[figure not shown]

Figure 1: (A-B) Whole-head MEG system with a specially designed bed and chair for measurements. (C) SQUID sensors. (D) Magnetically shielded room (MSR) to reduce environmental noise.

### **Resting State Measure**

Baseline brain activities will be measured for 5 minutes. The subject will be asked to remain still with eyes closed and rest.

## **Tasks**

### **Receptive Language Task**

We will follow the standard protocols according to the American Clinical Magnetoencephalography Society (ACMEGS) [64]. The language task corresponds to an adapted version [30] of the continuous auditory word recognition protocol previously described by Papanicolaou [23] for determining hemispheric dominance of language function. The subject will perform a practice session where they will be instructed to "try to remember" a set of five audibly spoken English words, deemed targets. Target words are as follows: *jump, little, please, drink, and good*. Depending on the subject's overall verbal memory capacity, the target words will be presented once or twice during the practice phase. Subsequently, during the MEG recording, the five target words will repeat in a different random order, mixed with a different set of 40 distractors (non-repeating words) in each of three blocks of stimuli. Words will be presented for 1 s, one at a time, and randomly varied with an interstimulus interval between 2 s and 3 s. The auditory stimuli will be delivered binaurally through two long plastic tubes terminating in ear inserts at an intensity of 60 dB sound pressure level (SPL) at the subject's outer ear. Target words correspond to four monosyllabic and one disyllabic word with a mean frequency in the G6-7 corpus of 158 occurrences per million (range: 32-194 occurrences) [65]. For distractors, 40% of words will be disyllabic and the remaining will be monosyllabic with a mean frequency of occurrence of 150 words per million in the same corpus (range: 18-820). The subject's task will be to listen to the words and lift their index finger of the dominant hand whenever they hear a repeated target word (one of the five). After the language task, the subject will be given a break.

### **Memory Task**

In this project, we will develop-use a widely deployednew procedure to study memory function using a visuospatial working memory (VSWM) task that will manipulate working memory (WM) load by using visual-stimulus complexity [55-59]. The task will be composed of a two-dimensional visual grid plane (see Fig. 2) segmented into nine regular squares, each of which might contain a symbol "O" or "+", otherwise empty. Only two symbols will be displayed in the grid. We will manipulate the WM load and congruency as follows: a) low WM load will only have one type of symbol with two apparitions in the grid (i.e., circles); b) high WM load will have two types of symbols with six apparitions in the grid (i.e., circles and crosses). Congruency will be manipulated by matched or unmatched encoding and retrieval stimuli. A total of 96 stimuli will be designed: 24 low-WM load-congruent; 24 low-WM load-incongruent; 24 high-WM load-congruent; and 24 high-WM load-incongruent.

[figure not shown]

Figure 2: Memory task; examples of experimental conditions. A: encoding stimulus; B: retrieval stimulus

Title: Pediatric Language and Memory Mapping in Refractory Epilepsy using Magnetoencephalography

PI: [name]

Site: Arkansas Children's Hospital

The symbols and grid plane will be white on a black background. The type font will be Arial with 80pp size. Each trial will begin with a central fixation cross-displayed for 300 ms, followed by encoding, maintenance, and retrieval phases. The symbols and grid will appear for 1 s (encoding phase), then a blank inter-stimulus interval (ISI) will display for 1.5 s (maintenance phase). Next, the symbols and grid will appear for 1 s (retrieval phase). The subject will be tasked with indicating whether the encoding stimulus matched the retrieval stimulus using two buttons; one for "congruent" and the other for "incongruent" response. Button type will be counterbalanced among subjects. The task will take around 16 minutes. The visual stimuli will be projected through an LCD projector onto a white screen located about 0.5 m in front of the subject and subtending 1.0-4.0 and 0.5 degrees of horizontal and vertical visual angle, respectively. A MEG compatible keyboard will be used to measure the subject's responses for "congruent" and "incongruent". The subject will practice the memory task before going to the MEG system using a computer from MEG laboratory. This practice phase will consist of a short version of the memory task with duration of approximately 4 minutes.

## **MRI**

MRI will be used to obtain individual anatomical brain information for MEG source reconstruction. MRI characteristics for MEG is a fast T1 scan containing tip of nose, both ears, and top of the head. If a previous MRI is available from medical records, we may use if it has the appropriate characteristics for MEG and if subject did not have any neurosurgery after this specific MRI. Otherwise, if no MRI is available, the subject will have an MRI scan of the brain.

## **Subject Withdrawal**

Participants may withdraw at any time for any reason, without penalty. No data will be collected about the subject following withdrawal from the study. Any subject withdrawing their consent to participate in the study or their authorization to use their protected health information will be withdrawn from the study. Additionally, the investigator may choose to remove subjects from the study for any reason.

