### ***Monitoring, Recording and Reporting of AEs***

All AEs occurring during the study period as previously defined must be recorded. All relevant historical medical conditions (as determined and documented by Investigator/Clinician that are known/diagnosed prior to the start of the study are to be recorded as medical history. Any medical condition that is present at the time that the subject is screened will be considered as baseline and not reported as an AE. However, if the study subject’s condition deteriorates or exacerbates at any time during the study, it will be recorded as an AE. Pre-existing conditions should be recorded as adverse events only if the frequency, intensity, or the character of the condition worsens during the study.

The clinical course of each event should be followed until resolution, stabilization, or until it has been determined that the study treatment or participation is not the cause. SAEs that are still ongoing at the end of the study period must be followed for up to 30 days to determine the final outcome. Any SAE that occurs after the study period and is considered to be possibly, probably, definitely, or related to the study treatment or study participation should be recorded and reported immediately to the Sponsor.

Title: Pediatric Language and Memory Mapping in Refractory Epilepsy using Magnetoencephalography

PI: [name]

Site: Arkansas Children's Hospital

All subjects will be monitored for AEs during the study. Assessments may include monitoring the subject's clinical symptoms; laboratory, pathological, radiological, or surgical findings; physical examination; or other appropriate tests and procedures.

AE data collection and reporting, which are required as part of every study, are done to ensure the safety of subjects enrolled in the studies and those who will enroll in future protocols. AEs are to be reported in a routine fashion at scheduled times during the trial, such as with the annual continuing review to the IRB. Certain AEs must be reported in an expedited fashion to allow for timely monitoring of subject safety and care.

The reporting of these events depends on the characteristics of the event:

1. Seriousness (grading of event)
2. Relatedness to use of the investigational device or study procedure
3. Expectedness

Steps to Determine if the Event Requires Expedited Reporting:

1. Identify the type of event
2. Grade the event using

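### The ban on collecting data after withdrawal conflicts with the required follow-up of a serious adverse event still open when a subject withdraws

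*Combined protocol and SAP*

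**What the plan says.** All references are to the combined protocol and SAP.

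**Subject Withdrawal.** Leaving is open to subjects throughout: "Participants may withdraw at any time for any reason, without penalty". The data rule comes next: "No data will be collected about the subject following withdrawal from the study". The section then says that a subject who revokes consent, or authorization to use health information, will be withdrawn. It closes: "Additionally, the investigator may choose to remove subjects from the study for any reason". No data rule is attached to removal, and nothing in the section mentions adverse events.

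**Monitoring, Recording and Reporting of AEs.** For events in general: "The clinical course of each event should be followed until resolution, stabilization", or until the study has been ruled out as the cause. For serious events: "SAEs that are still ongoing at the end of the study period must be followed for up to 30 days to determine the final outcome". An SAE that arises after the study period and is considered related "should be recorded and reported immediately to the Sponsor". A note in the same section brings in events up to 30 days after the last protocol procedure.

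**Expedited Reporting of AEs.** All deaths go to the Sponsor, related or not, no later than 48 hours after they become known.

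**Definitions, under Adverse Events.** Events are recorded from consent to the end of the study procedure, in the medical record, on the case report forms and in the adverse event log.

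**The concern.** One rule stops data collection when the subject leaves, and the other requires data collection to continue. Neither mentions the other. Staff with a withdrawn subject and an unresolved SAE would have to breach one of them.

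The situation is foreseeable on the protocol's own terms. The subjects have drug-resistant epilepsy, and event recording starts at consent. The SAE definition gives convulsions without hospitalization as an example of an important medical event. The risk section names claustrophobia, anxiety and dizziness as possible effects of MRI. The same event could therefore be recordable and be the reason a subject leaves. Not every seizure would qualify, because a pre-existing condition counts as an adverse event only if it worsens.

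At stake is the record of how such an event developed and ended, in a pediatric study whose first aim is feasibility.

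**Working it through.** No calculation applies; this is a check of one text against another. The plan gives no figure on this point to reproduce.

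**1. The two rules side by side**

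| | Subject Withdrawal | Monitoring, Recording and Reporting of AEs |
|---|---|---|
| What it governs | Any data about the subject after withdrawal | Course and outcome of adverse events |
| Force | Flat prohibition | Mandatory for SAEs still open at the end of the study period; advisory for other events |
| Duration | Nothing after withdrawal | Up to 30 days for open SAEs; to resolution, stabilization or a finding of no causal link for others |
| Exception for the other rule | None | None |

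**2. Do the time windows overlap?** The 30 days run from the end of the study period, which the definitions tie to the end of the MEG tasks, or to the MRI if one is needed. The protocol does not say when that period ends for a subject who leaves part-way. Whether it is taken as the moment of leaving or the later date when procedures would have finished, the follow-up falls after withdrawal. A subject who finishes all procedures and then withdraws with an SAE still open is caught in the same way for the days that remain.

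**3. Who is caught?** A subject or guardian who withdraws with an open SAE is caught expressly. Investigator removal is less certain. It stands under the same heading, is introduced as an addition, and has no data rule of its own. The section also speaks of subjects being withdrawn, so the term is not confined to the subject's own act. Treating removal as withdrawal is therefore the natural reading, but the text does not state it.

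**4. Is there an exception elsewhere?** I looked through the whole Adverse Events section, Data Handling and Recordkeeping, and Ethical Considerations. Data Handling covers only how to ask to withdraw and how to take data out of future research use. None of these sections exempts safety data from the ban or withdrawn subjects from follow-up.

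**5. What would be lost?** An event that leads to withdrawal comes before it. Its onset is recordable on the case report form and in the log, and a potential SAE must be notified promptly to the Sponsor. What the ban removes is its later course, any worsening, its outcome, and any related SAE that arises afterwards. It also cuts across the reporting of later events and deaths. I rest nothing on the 30-day note alone, because it names a procedure that this protocol does not otherwise describe.

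**The case against.** **The ban may not reach investigator removal.** It follows the sentence on participants withdrawing, whereas removal comes later with a different verb. This stands as a limit. A reader might infer that every route out of the study ends safety follow-up, but the text does not say so. The conflict does not depend on it, because a subject's own withdrawal is enough.

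**Stopping a scan is not withdrawing.** A child who stops because of distress may stay enrolled, and the protocol offers breaks. This stands: such a child remains under the adverse event rules alone.

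**Ending collection may be intended when consent or authorization is revoked.** This is plausible. The section does not separate that case from others, so it is a reason to clarify the rule rather than leave it.

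**The event itself is not lost.** This stands. A reader might infer that the safety record would look cleaner than it is, with events selectively missing. The documents do not support that: event counts, seriousness and onset are unaffected for events before withdrawal. The gap is in outcomes and later developments.

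**The consent form may already deal with this.** Consent pages were not available for this review, so that cannot be ruled out. It would not remove the contradiction within the protocol.

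**Conclusion.** The concern holds in a limited form. The withdrawal rule and the adverse event rules cannot both be followed for a subject who withdraws with an open SAE. Because the follow-up duty is mandatory for SAEs, the contradiction is firm there; for other adverse events it is softer. Extending it to subjects removed by the investigator assumes that removal counts as withdrawal.

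For an affected subject, recorded follow-up after withdrawal falls from as much as 30 days to none. That is the only size the documents support. A reader might express one such case as a share of the sample: 1/15 = 6.7% using the Study Population section, or 1/10 = 10% using Study Design and Procedures, since the two sections give different sample sizes. That is the weight of one assumed subject and says nothing about how often this would happen. Nor do the documents support an inference that withdrawals will mostly be caused by events. They give no rates or reasons for withdrawal, and consent precedes a separately scheduled visit, so a subject may leave before any procedure.

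The practical effect is probably small, with one MEG session, possibly one MRI and no treatment. It concerns the completeness of safety follow-up and does not touch the source imaging or the hemispheric comparison. The point still merits correction, because it is a stated rule that would cause required SAE outcomes to go unrecorded.

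**What to change.** Reconcile Subject Withdrawal with the Adverse Events section. Whether safety follow-up continues after withdrawal is for the sponsor and the investigator to settle. One wording that would resolve the conflict is:

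*After withdrawal or removal, no further study procedures will be done and no further research data collected. Adverse events and SAEs that began before that point will still be followed and recorded as set out under Adverse Events, to the extent that any withdrawal of consent or authorization allows.*

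The amendment should also:

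- say expressly whether removal by the investigator is covered;
- say how the reporting of later related SAEs and of deaths applies to subjects who have left;
- carry a matching cross-reference in the adverse event section;
- align the consent form, if it does not already say this.

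The cost is a short protocol amendment and, if needed, matching consent wording. The small downside is some record review for a withdrawn subject with an open event. This should be light, since subjects belong to the same hospital's epilepsy program and events are already captured in its electronic record.
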